#### 1.5 Dose Rationale

Others have treated mice with Fisetin 50 mg/kg/day for weeks without evidence of toxicity. We treated 4 male and 4 female 8 month old C57/Bl6 mice with Fisetin 500 mg/kg/day (25-fold higher than the dose to be used in this clinical trial) by oral gavage for 2 consecutive days compared to 4 male and 4 female mice treated with vehicle. We found no evidence of substantial toxicity, as assessed by monitoring activity, food intake, and respiratory quotient in metabolic cages (Comprehensive Laboratory Animal Monitoring System, Columbus Instruments) for 48 hours after the last Fisetin dose. We administered 100 mg/kg/day for 2 consecutive days by mouth as daily pulse doses, 5 times the dose proposed in in this clinical trial, to 2 older Rhesus monkeys (ages 19 and 28 years, which is old for this species) at the National Primate Center. In over 1 month of close monitoring, neither monkey had adverse effects such as reduced appetite, altered activity, vomiting, or diarrhea. Acknowledging the higher rates of drug metabolism in mice compared to humans and differences in physiology between non-human primates and humans, in an effort to avoid side effects, a daily dose of ~20 mg/kg was selected here. We verified that this dose is sufficient to reduce senescent cell burden in mice. Our studies in very old coronavirus-infected mice demonstrated that this dose of Fisetin dramatically enhances survival (Figs. 22, 24, 26, 28, and 29). We will administer this dose, 20 mg/kg/day for 2 consecutive days, at Days 0 and 1 and 8 and 9, since senescent cells can re-accumulate by 10 days, at least in culture, and mortality rises several days after completing the first round of Fisetin in mice (Fig. 28). We found anti-CoV antibodies in old mice by 16 days after initiating Fisetin treatment. Hence, here two courses of 2 consecutive days of Fisetin 20 mg/kg/day will be administered, as in mice in Fig. 29).

#### 1.6 Risks and Benefits

There appear to be few, if any, risks of Fisetin at the doses to be used that we have evidence for, provided the subjects meet the exclusion criteria in the protocol regarding medications that Fisetin could interfere with. We have not seen serious or severe adverse events so far in elderly frail women enrolled in our AFFIRM studies from Fisetin 20 mg/ kg/ day for 2 consecutive days in the over 50 subjects randomized to Fisetin or placebo. We did not see adverse effects such as altered food intake, weight, or behavior in old *Rhesus* macaques given 5 times the dose proposed here or in mice given 25 times the dose. Fisetin has been widely sold as a nutritional supplement in 100 and 500 mg capsules for many years by Amazon and other vendors without prescription and without any reported side effects that we could find.

Based on our studies in mice, there may be decreased morbidity and mortality due to  $\beta$ coronavirus infection after Fisetin administration. All subjects in this study will be elderly and

have proven CoV infection that could progress to severe or critical disease. The potential benefit to individual subjects in this trial and other people might be large and risks from Fisetin are low or negligible.

In this study, we will examine the effect of oral/ enteral Fisetin as a senolytic agent in humans, which may have immense potential for and reducing frailty/ physical dysfunction and inflammation and alleviating morbidity and mortality from CoV or other infections in older subjects and those with other conditions and diseases associated with accumulation of senescent cells. As an additional, advantageous, off-target effect, removal of senescent cells may allow for functional improvement of neighboring or distant tissues and cells, including MSC's, accelerating recovery. We found that senolytics restore function of MSC's. Our collaborator, [name], working with investigators in China, noted that transplanting healthy MSC's can alleviate symptoms and signs in severely ill CoV-infected patients. Thus, an additional benefit of senolytics for CoV could be this alleviation of stem cell and progenitor dysfunction.

Based upon review of the published literature and our pre-clinical data, we do not anticipate the occurrence of serious adverse events with the prescribed regimen in this study. We have identified a variety of drug-drug interactions (*e.g.*, current use of warfarin) for which we established exclusion criteria or modification plans to minimize associated risks. We could find no reports of Fisetin toxicity in the literature. Some flavonols have been associated with DNA damage *in vitro*, but Fisetin exerts little or no genotoxic effects. To the contrary, Fisetin has been noted to be anticarcinogenic. Indeed, we found that chronic Fisetin administration delays cancer in mice and increases remaining lifespan in old mice as well as increasing lifespan of DNA damage/ genotoxicity highly-prone  $Ercc1^{-/\Delta}$  mice by over  $17\%^{59}$ . Since up to 50% of most mouse strains die from cancers, this shows that the beneficial effects of Fisetin on such procarcinogenic factors as senescent cell burden and tissue chronic inflammation appear to more than counteract any theoretical effects of flavonol-associated genotoxicity. **Fisetin actually reduces cancer risk**, as opposed to increasing it.

Overall, we do not anticipate substantial risk from the natural product, Fisetin, which is present in many foods, including cucumbers, strawberries, and other fruits and vegetables, albeit at levels lower than will be used here. CoV infection causes 25 to 50% mortality in nursing home patients. Thus, the risks of using this drug are likely minimal compared to the anticipated benefits for nursing home patients with a limited life expectancy, even without CoV infection.

## 2 Study Objectives

#### 2.1 Primary Objectives

The primary objective is to test the efficacy of the senolytic drug (Fisetin) in preventing or delaying progression of CoV severity in nursing home patients with proven CoV according to a 7 point scale for nursing home CoV severity adapted from the WHO Ordinal Scale for Clinical Improvement of CoV\*:

- Not hospitalized nor on additional oxygen (compared to baseline), at baseline level of function (as assessed by activities of daily living).
- Not hospitalized nor on additional oxygen, but below previous level of function.
- Hospitalized or moved to a more intensive unit within the nursing home because of additional dysfunction (not simply because of positivity), but not requiring additional oxygen nor placed on an antiviral drug for worsening CoV symptoms.
- Hospitalized or moved to a more intensive unit within the nursing home and requiring additional oxygen (vs. baseline) and/ or placed on an antiviral drug for worseningCoV symptoms.

- Hospitalized or moved to a more intensive unit within the nursing home and requiring additional oxygen by ECMO or ventilator.
- Transferred to palliative care to provide end-of-life care.
- Death.

\*The WHO Ordinal Scale for Clinical Improvement of CoV (Appendix 1) is scored from 0 to 8 with 0 = no evidence of infection to 8 = death. Our adapted scale does not include scores 0 or 1, since no subjects in COVID-FIS will meet these criteria (e.g., all subjects have proven CoV infection, so none have "no infection").

#### 2.2 Secondary Objectives

A secondary objective is to assess the safety and tolerability of oral/enteral Fisetin in older nursing home residents. These elderly adult nursing home residents will have proven CoV infection.

Further objectives are to test the efficacy of the senolytic drug (Fisetin) in preventing, delaying, or alleviating physical dysfunction (frailty and other functional parameters in the MDS which is completed every quarter or 100 days for nursing home residents nationally), inflammation; 2), reducing senescent cell abundance in blood, increasing oxygen requirement (assessed by changes in daily mean skin pO2 as a function of inhaled oxygen [SpO2]/FiO2), decreasing escalation in oxygenation device, intubation, non-invasive ventilation, cytokine storm/ ARDS/ myocarditis with troponin leak, death, delayed recovery, poor clinical condition, and progression to fibrotic lung disease and enhancing antibody response using data available from nursing home/ hospital records and data and samples from subjects collected where feasible.

## 3 Study Design

#### 3.1 General Description

This study is a pilot, randomized, placebo-controlled, multi-site study of Fisetin in elderly nursing home participants. A total of 250 participants will be enrolled in this study. Study staff and participants will be blinded with regards to groups. Subjects will be randomized to placebo or treatment. Fisetin 20 mg/kg/day or placebo will be made available by the study staff for oral or enteral administration on study Days 0, 1, 8, and 9.

If Remdesivir or another anti-viral agent or immunization should become standard of care in nursing home CoV patients (*e.g.*, approved by the FDA) during the study, patients being treated with such agents may be enrolled, with randomization stratified based on whether subjects are on such an anti-viral agent. We conducted studies of mice (N=6 old mice; age 22.9±0.7 months [means±SEM]; females) on higher doses of Fisetin than to be administered here (100 mg/ kg/ day for 2 days) by gavage and Remdesivir (50 mg/ kg/ day) i.p. We did not find Fisetin plus Remdesivir resulted in increased toxicity (changed body weight, food intake, activity, grooming, appearance, or frailty score) during any of the 4 days following administration *vs.* Remdesivir alone (Table 3; 100 mg/ kg/ day for 2 days by gavage; N=6 old mice; age 23.4±0.7 months). Therefore, if patients already in COVID-FIS are started on Remdesivir, they will not be withdrawn from the study. During statistical analyses, patients will be analyzed regarding Remdesivir administration *post hoc.* 

Table 3. Remdesivir + Fisetin is Not More Toxic than Remdesivir Alone

Treatment	Age (Mo.)	Frailty Score	Body Wt. (g)	Body Temp. (°C)	Body Wt. (g)	Frailty Score	Body Wt. (g)	Body Temp. (°C)	Body Wt. (g)
Date	5/4	5/4	5/4	5/4	5/9	5/10	5/10	5/10	5/11
RDV+Fisetin	25.03	0.357	27.2	31	26.00	0.37	25.7	31.73	26.1
RDV+Fisetin	22.20	0.125	34.2	32	34.9	0.185	33.8	32.07	34.1
RDV+Fisetin	22.35	0.143	30.1	32	28.5	0.259	27.6	32.83	28.2
RDV+Fisetin	19.47	0.21	29.5	32	27.3	0.278	27.6	31.9	27.8
RDV+Fisetin	24.18	0.20	42.2	32	41.5	0.204	39.8	30.9	39.7
RDV+Fisetin	24.18	0.161	28.3	31.7	27.9	0.204	27.9	32.17	28.3
Mean	22.90	0.2	31.9	32	31.02	0.25	30.4	31.93	30.7
SEM	0.752	0.031	2.08	0.14	2.24	0.026	2.00	0.24	1.93
RDV	24.01	0.214	27.6	31.7	27.1	0.241	26.6	31.67	26.8
RDV	23.59	0.232	27.9	32.1	27.9	0.296	27.8	32.6	28
RDV	22.20	0.268	30.9	31.6	29.9	0.241	29.1	32.3	29.3
RDV	22.20	0.125	34.5	32.4	34.1	0.185	33.8	32.77	33.5

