# 3.2 Number of Subjects

Enroll and screen 250 subjects to accrue and randomize 150 men and postmenopausal women aged  $\geq$ 65 years old to be administered Fisetin (N=75) or placebo (N=75).

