# 5.3 Method for Assigning Subjects to Treatment Groups

Subjects will be randomized to either Fisetin or placebo using an internet-based, web browser randomization procedure maintained by the data management team at Wake Forest School of Medicine. Study coordinators access the randomization application through the trial website. Access to this application is password-protected and its communications are encrypted. Once security requirements are satisfied, consent and eligibility of the participant are verified, and randomization will occur. Randomization is controlled centrally based on each potential participant's consent and eligibility status. ONLY eligible participants will have the randomization button displayed. It will be impossible to randomize an ineligible person, or a person for whom screening or consent is incomplete. We will use a permuted block randomization scheme with varying block sizes and without stratification so that group assignment is balanced as the study proceeds, but study personnel will not be able to predict treatment assignment.

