# 6.1 Screening Visit (Days -2 to 0)

Patients will be pre-screened prior to being recruited for the study. Subjects will be screened within 3 days before randomization to determine eligibility for participation in the study.

Written informed consent will be obtained from the nursing home resident or from a Legally Authorized Representative (LAR) who can provide informed consent. Sections B to E (B: Hearing, Speech, and Vision, C: Cognitive Patterns, including the Brief Interview for Mental Status, D: Mood, and E: Behavior) of the most recent (within the last 100 days) Minimum Data Set (MDS) will be utilized to determine participants' ability to provide a truly informed consent and such an ability should be verified by staff with access to the nursing homes (e.g., Medical or Nursing Director, nurse practitioner, physician's assistant) and if the participant is not able, their LAR will be asked. All MDS datasets for each subject will be collected throughout their inclusion in the study (up to 194 days) and the date(s) and type of vaccinations for CoV will be recorded.

In the pandemic situation where access to nursing homes and hospitals is limited, if allowed, digital/electronic consent will be obtained from the patient's LAR and will be documented by the investigator or the authorized designee. For any subject, it is the responsibility of the investigator or study team member to obtain consent prior to performing any protocol-mandated assessment.

After the informed consent and agreement by the patient's nursing home attending physician, nurse-practitioner, or physician's assistant, the following assessments are performed to determine eligibility requirements as specified in the inclusion and exclusion criteria. Assessments performed as part of the routine care of the subject by nursing home staff may be used to assess eligibility.

- Demographics.
- Focused medical history including the following information if feasible: date of first symptoms, overall symptoms, exposure source, demographics, baseline characteristics, allergies, medical history, reasons for nursing home admission (diagnoses, key symptoms and signs at and since admission as abstracted from the most recent MDS or available nursing home records).
- Determination of Ordinal Scale score.
- Review of concomitant medications including any COVID-19 vaccinations.
- Review of adverse events.

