# 8 Statistical Plan

### 8.1 Sample Size Determination

Power calculations for the comparison of the Fisetin and control groups were made assuming an equal distribution among the 7-point scale categories at Day 14 among the controls using a two-sided significance level of 0.05 (alpha). With 75 subjects per group, the study would have 80% power to detect a log odd's ratio of 0.81 which translates to an odd's ratio of 2.25 comparing the control to Fisetin group. Power calculations were run using the PASS software package.

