#### 8.2 Statistical Methods

All participants who are randomized will be included in the primary efficacy analysis. The analysis will follow the ITT principle (*i.e.* according to the treatment arm they are randomized to). For the primary analysis using the values of the 7-point scale, we will test the coefficient of the treatment effect (as a fixed effect) in an ordinal logistic regression model using a 2-sided 0.05 level Wald test after adjusting for key baseline variables such as baseline COVID severity status, age, and sex that show imbalance between the groups. Subjects who withdraw early but received at least some treatment will have their last known values carried forward until they complete the study at Day 180±14. All participants who receive any dose of drug (Fisetin or placebo) will be included in the safety and tolerability evaluation. The definitions of adverse events are described in Sections 9.1-9.3. Participants will be assessed over the entire period of drug administration. Frequency tables will be generated to summarize the occurrence of AE's by treatment arm. Comparisons of the rates of individual AEs will be done using tests of proportions such as the Fisher's exact test or Chi-squared test.

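### Vaccination status is collected, but the plan never commits to using it: covariates enter the primary model only if they look imbalanced, which forgoes a possible power gain

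*Combined protocol and SAP*

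**What the plan says.** - **Who may enter (3.1).** The section allows for a change in care: "If Remdesivir or another anti-viral agent or immunization should become standard of care in nursing home CoV patients". Such residents may be enrolled, "with randomization stratified based on whether subjects are on such an anti-viral agent". Immunization is part of the trigger but is not named as a stratum.
- **What is collected (6.1, 7.5, Appendix 2).** Section 6.1 says "the date(s) and type of vaccinations for CoV will be recorded". Appendix 2 asks for any COVID-19 vaccination to be recorded with concomitant medication. Section 7.5 plans antibody tests partly to look at vaccine response, so vaccinated participants are expected.
- **Randomisation (5.3).** "We will use a permuted block randomization scheme with varying block sizes and without stratification".
- **Primary model (8.2).** An ordinal logistic regression with a two-sided Wald test of treatment, "adjusting for key baseline variables such as baseline COVID severity status, age, and sex that show imbalance between the groups". No threshold for imbalance is given.
- **Secondary models.** The logistic and Cox models adjust for unspecified other factors of interest. The demographic factors listed for study are age, sex, race and ethnicity.
- **Power (8.1).** "80% power to detect a log odd's ratio of 0.81 which translates to an odd's ratio of 2.25", with 75 per group and equal probability in the seven control categories at Day 14.

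**The concern.** Vaccination is a baseline variable that plausibly predicts the seven-point severity outcome, and the trial already collects it with dates. Whether it reaches the primary model is left to an observed imbalance.

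That rule has two faults, and both apply equally to severity, age and sex. First, the primary model is not fixed before the data are seen. Second, the rule answers the wrong question. In an ordinal logistic model, omitting a prognostic covariate pulls the treatment odds ratio towards 1 and lowers power even when the arms are perfectly balanced on it. A rule triggered by imbalance leaves the covariate out in exactly those cases.

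At stake is some power in a design with no visible slack: 8.1 states no inflation for dropout, and 4.4.6 does not replace subjects who withdraw consent.

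**Working it through.** **Inputs from the documents.** 75 per arm (3.2); two-sided alpha 0.05, log odds ratio 0.81 and control probability 1/7 in each category (8.1). exp(0.81) = 2.248, so the 2.24 in the Study Summary and the 2.25 in 8.1 differ only by rounding.

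**Assumed inputs, not in the documents.** Share vaccinated, 50% to 95%. Vaccine odds ratio on the seven-point scale, 1.5 to 5 (1 means not prognostic).

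**Step 1: reproduce the stated power.** Whitehead's proportional-odds formula, with p̄ the category probabilities averaged over the arms:

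n per arm = 6(z₀.₉₇₅ + z₀.₈₀)² / [(log OR)² (1 − Σp̄³)]

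A log odds ratio of 0.81 gives Fisetin-arm probabilities 0.2725, 0.2009, 0.1542, 0.1221, 0.0991, 0.0820 and 0.0690, so Σp̄³ = 0.0240.

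- n = 6 × (1.960 + 0.842)² / (0.6561 × 0.9760) = 73.5 per arm.
- At n = 75: 0.81 × √(75 × 0.9760/6) = 2.829, and Φ(2.829 − 1.960) = 80.8%.
- A Wald calculation on expected cell counts gives a standard error of 0.2925: 0.81/0.2925 = 2.769, and Φ(2.769 − 1.960) = 79.1%.

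Both are within 2 points of 80%. The figure in 8.1 stands as an unadjusted two-group calculation.

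**Step 2: power without and with vaccination in the model, if 0.81 is the within-stratum log odds ratio.** Cut-points were solved so that the control margin stays at 1/7 per category. Both models were fitted to expected cell counts, and power = Φ(estimate/SE − 1.960).

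| Vaccinated | Vaccine OR 1.5 | OR 2 | OR 3 | OR 5 |
|---|---|---|---|---|
| 50% | 78.4 → 79.0 | 77.2 → 79.0 | 74.4 → 78.9 | 69.3 → 78.6 |
| 80% | 78.7 → 79.1 | 77.9 → 79.0 | 76.2 → 79.0 | 73.1 → 78.8 |
| 90% | 78.9 → 79.1 | 78.4 → 79.1 | 77.5 → 79.0 | 75.8 → 78.9 |
| 95% | 79.0 → 79.1 | 78.7 → 79.1 | 78.2 → 79.0 | 77.4 → 79.0 |

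Worked cell (50%, OR 3): the unadjusted odds ratio falls to 2.146, log 0.764, SE 0.2917, and Φ(2.618 − 1.960) = 74.4%. Adjusted: 0.81/0.2933 = 2.762, and Φ(0.802) = 78.9%.

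A separate simulation (1,500 trials per scenario) agrees in direction and roughly in size: 78.1 → 80.4 for OR 2 at 50%, 74.7 → 80.1 for OR 3 at 50%, and 77.5 → 79.7 for OR 3 at 80%, with Monte Carlo error of about 1 point.

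**Step 3: the same, if 2.25 is the marginal effect.** Unadjusted power stays at 79.1%. Adjustment raises it to between 79.2% (OR 1.5, 95% vaccinated) and 87.1% (OR 5, 50% vaccinated).

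**Step 4: how often would an imbalance rule bring vaccination in?** Under unstratified 1:1 allocation, the standard deviation of the difference in share vaccinated is √(2p(1 − p)/75). The chance of a difference of 10 points or more is 22% at p = 0.5 (SD 8.2 points), 13% at p = 0.8 (SD 6.5) and 4% at p = 0.9 (SD 4.9). The 10-point threshold is illustrative, since 8.2 gives none.

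**The case against.** The strongest case against acting has four parts.

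- **The list is open.** The covariates in 8.2 are examples, and the secondary models leave their adjustment factors unspecified. A reader might infer that vaccination is shut out of every efficacy model; the text does not say so. This stands: vaccination is uncommitted, not barred.
- **The power statement is not undermined.** A reader might infer that 80% is reached only with vaccination in the model. Section 8.1 describes a two-group calculation without covariates, so 2.25 reads most naturally as a marginal effect. Adjustment is then a gain above plan (step 3), not a rescue of it. This stands.
- **The size rests on outside inputs.** Coverage and vaccine effect are assumed, and the gain is 1 point or less in several cells of the table. No severity term was included, although severity is the first covariate named in 8.2. If vaccination acts partly through severity at entry, its added value is smaller than shown. This stands too.
- **The supporting text is thinner than it looks.** Immunization in 3.1 is conditional, so it is not stated as a change that has occurred. The reference in 3.1 to infection despite immunization concerns possible later trials. A vaccinated share that drifts over accrual does not by itself bias the comparison, because permuted blocks keep the arms balanced over time.

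None of this defends the imbalance rule itself. In the calculations on expected counts, adjustment did not lower power at any assumed value. Singling out vaccination could look like preference, which is why the change below fixes the whole covariate set.

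**Conclusion.** The point holds as a missed, cheap improvement and a data-dependent covariate rule, not as an error in the sample size. Vaccination dates and type are collected, vaccinated participants are expected, and neither 5.3 nor 8.2 commits to using the information.

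If 2.25 is the within-stratum odds ratio, the gain from adjustment is:

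- roughly 0 to 2 points for a vaccine odds ratio of 2 or less, or for coverage of 95% or more;
- about 3 to 9 points mainly for odds ratios of 3 to 5 with 50 to 80% vaccinated;
- zero if vaccination is not prognostic in these already infected residents, and smaller than tabulated if baseline severity carries part of the same information.

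If 2.25 is marginal, unadjusted power is as planned and the gain, 0.1 to 8.0 points, lies on top of it. The direction does not depend on the assumed values, provided that vaccination is prognostic; the size does.

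**What to change.** In 8.2, before unblinding:

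1. Name vaccination status at randomisation as a fixed covariate in the primary ordinal model, together with baseline severity, age and sex. A binary vaccinated/unvaccinated term using only doses dated before randomisation is enough. It avoids a months-since-dose variable that has no value for the unvaccinated. State how unknown status or dates are handled.
2. Delete the condition that covariates enter only if they show imbalance.
3. Use the same terms in the secondary logistic and Cox models.

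This takes a sentence or two and no new data. The vaccination term costs one or two degrees of freedom. Stratifying the randomisation by vaccination without adjusting for it would add little, since the gain comes from the term in the model.

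Separately, 3.1 (stratified by anti-viral agent) and 5.3 (no stratification) contradict each other and must be reconciled.
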